147 5.6% total body weight, with 22.7% excess BMI lost [delta BMI/(initial BMI-25)] over the 3-
148 month monitoring period. Participants reported decreases in appetite following the procedure at
149 all time points, with 15.8% reporting “somewhat less appetite”, 68.4% reporting “much less
150 appetite”, and 10.5% reporting “very much less appetite.”⁴³

151

152 In addition to weight loss, we anticipate that the cryovagotomy procedure will result in
153 significant improvement in glycemic control and cardiovascular risk factors, which may result in
154 long-term benefit is reducing diabetic complications. We propose a prospective, randomized
155 controlled trial to determine if a minimally invasive cryoablation procedure of the vagus nerve
156 will lead to greater weight loss and improvements in glycemic control, metabolic profile, and
157 cardiovascular risk factors compared to lifestyle intervention in obese patients with T2D. Our
158 data will provide preliminary data to support application for an NIH grant to further investigate
159 manipulation of the gut-brain axis for management of type 2 diabetes and obesity.

160

161 **III. DESCRIPTION OF STUDY PROTOCOL**

162

A. SPECIFIC OBJECTIVES:

163 **Objective 1. To compare glycemic control of patients undergoing vagus nerve cryoablation**
164 **plus lifestyle intervention at 6 and 12 months compared to lifestyle intervention alone in**
165 **obese patients with T2D.** Patients with T2D, BMI 30-40 kg/m², A1c 7.5-10.5% on stable doses
166 of oral antidiabetic agents will be randomized to cryoablation plus lifestyle or lifestyle
167 intervention alone and will be followed prospectively for 12 months in a controlled randomized
168 trial. We will compare changes in A1c levels between groups at 3, 6 and 12-months of follow up.
169

170 **Objective 2. To determine changes in weight and anthropometric metrics among patients**
171 **receiving cryoablation plus lifestyle intervention versus lifestyle intervention only.** Changes
172 in body weight, BMI, waist circumference, and BIA measured at baseline, 3 and 6 months after
173 intervention will be assessed.

174
175 **Objective 3. To determine safety of the cryoablation of the vagus nerve.** We will monitor
176 rates of AEs and SAEs related to the procedure which develop during the duration of the trial.
177

178 **B. ENDPOINTS:**

179 The primary endpoint of the trial is difference in glycemic control, defined as A1c, fasting

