216 guided cryoablation of the vagus nerve plus lifestyle intervention or lifestyle intervention alone.

217 **Group 1:** CT guided cryoablation of the vagus nerve plus lifestyle intervention (n=15).

218 **Group 2:** Lifestyle intervention by trained RD/CDE (n=15).

219 All subjects will have the procedure performed at Grady Memorial Hospital or Emory University
220 Hospital Midtown or Johns Creek by trained study personnel.
221

222 The study schema is shown below. Both groups will undergo screening for eligibility followed
223 by randomization. If the subject is not fasting at time of initial consent and screening, he/she will
224 be brought back for a subsequent visit with fasting blood work. Subjects must be randomized
225 within 4 weeks of the screening visit. If the randomization visit falls outside of the 4 week time
226 frame, the subject must undergo repeat screening procedures. In- person lifestyle counseling will
227 be provided at baseline visit for both groups. Those undergoing cryoablation will receive a phone
228 call 24 hour post-procedure to evaluate for any immediate complications, 1 week in person
229 follow up visit, as well as a safety call at 2 months. Subjects in both groups will have weekly
230 contact with RD and in person follow up visits at 4 weeks, 3 months, and 6 months. Blood work,
231 anthropometric data and questionnaires will be administered at baseline, 3 months, and 6 months.
232 Safety follow up appointments will be scheduled at 9 months and 12 months, though no further
233 lifestyle counseling will be provided after 6 months. Questioning regarding adverse events and
234 side effects will occur at all visits, as well as assessment of glycemic control. Anti-
235 hyperglycemic medications will be adjusted at visits under the direction of the endocrinologist,
236 or as needed for clinically significant hypo- or hyperglycemic events.

237
238

239 Blood work will be as follows: For all lab parameters, subject results must be within the
240 reference range unless otherwise specified by inclusion/exclusion criteria or if assessed by study
241 physician to be not clinically significant.

Lab test	Baseline	3 months	6 months	9 months	12 months
Complete metabolic panel	X	X	X	X	X
Pregnancy test	X	X	X	X	
HbA1c	X	X	X	X	X
Lipid panel	X		X		
Insulin level	X	X	X		X
TSH	X				

242
243

D. STUDY PROCEDURE:

244 **Cryoablation procedure (to be performed by [name] or [name]):** Subjects will

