357 adjusted. Subjects on metformin will have the dose titrated to a maximum of 2000 mg/d if
358 tolerated. Sulfonylureas can be titrated to maximal doses per manufacturer instruction. Subjects
359 may be prescribed rescue therapy with insulin in the event of significant hyperglycemia
360 unresponsive to titration of oral agents. In the setting of BG <100 mg/dl, sulfonylurea doses will
361 be decreased by 50% and discontinued if necessary. If BG <55 mg/dl, sulfonylureas will be
362 stopped. Metformin will be stopped if hypoglycemia persists.

363

364 **Technical success rate of the procedure and procedure related complications:**
365 Discontinuation of the trial will occur if 3 participants within the first 8 of 30 planned experience
366 significant adverse events (AEs) (Grade 3 procedure-related AE or procedure-related serious
367 AE) at any point during follow-up and if 4 participants experience significant AEs (Grade 3
368 procedure-related serious AE) at any time. The trial will be stopped at any point if a Grade 4 or
369 Grade 5 AE occurs until determination can be made regarding its potential relationship to study
370 involvement.

371

372 **Grading of AEs:**

373

Grade 1	Mild; asymptomatic or mild symptoms; clinical or diagnostic observations only; intervention not indicated
Grade 2	Moderate; minimal, local or noninvasive intervention indicated; limiting age-appropriate instrumental ADL
Grade 3	Severe or medically significant but not immediately life-threatening; hospitalization or prolongation of hospitalization indicated; disabling; limiting self-care ADL
Grade 4	Life-threatening consequences; urgent intervention indicated
Grade 5	Death related to AE ⁶⁷

374

375 Specific clinical signs or symptoms that will qualify for the above criterial include (amongst
376 other potential Grade 3-5 AEs not listed here): constitutional symptoms (severe fatigue
377 interfering with ADLs, fever $> 40^{\circ}\text{C}$, prolonged and/or severe rigors), endocrine (uncontrolled
378 hyperglycemia, ketoacidosis), gastrointestinal (inadequate caloric intake requiring TPN or IV
379 fluids, diarrhea requiring IV fluids and/or manifesting as >7 stools/day, symptomatic abdominal
380 distention or bloating, severe abdominal pain requiring narcotics, ileus, severe nausea requiring
381 hospitalization, bowel obstruction or perforation), hemorrhage requiring intervention, infection
382 requiring antibiotics, or pain interfering with ADLs.

383

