21. History of autonomic dysfunction, including amyloidosis, Parkinson's disease, autoimmune disease, spinal cord injury

G. STATISTICAL CONSIDERATIONS:

464 The primary outcome is the difference in glycemic control (as measured by HbA1c) at 6 and 12
465 months between the vagus nerve cryoablation group and the lifestyle intervention group.
466 Summary statistics including mean, median, and standard deviations for the changes in HbA1c
467 at 3, 6, 9 and 12 months will be computed. We will then compare the changes at 6 months
468 between the two treatment groups by a nonparametric Wilcoxon test or a two-sample t-tests
469 (with appropriate data transformation if needed). We will conduct one-way ANOVA to estimate
470 the mean difference in glycemic parameters at 6 and 12 months month between the two
471 treatment groups. We may further adjust for some important confounders by using linear
472 regression models. We will also assess the glycemic control outcomes simultaneously across
473 different follow-up visits (i.e. 12, 24 weeks) through repeated measures ANOVA models, which
474 appropriately account for within-subject correlations in the measurements. In addition, we will
475 consider repeated measures linear regression model with visits incorporated as a continuous time
476 variable. We may include other covariates in the model when feasible.

477 The primary safety endpoint of the trial is the occurrence of death and all procedure related
478 complications, such as bleeding, infection, pneumothorax, hemothorax, pulmonary injury,
479 complications of sedation, pain requiring hospital admission or treatment, dysphagia,
480 gastroparesis, nausea and vomiting, and gastrointestinal ulceration for the duration of the study.
481 We will first use the Chi-square test (or Fisher's exact test) to compare the occurrence of this
482 primary safety endpoint between the two treatment groups. We will perform logistic regression
483 to evaluate the group difference while adjusting for other potential confounders such as age,
484 gender, and BMI. In addition, we will compare the number of procedure related complications
485 by using Poisson regression or Negative Binomial regression between the two treatment groups.
486 Standard model selection (e.g. forward, backward variable selection) and model checking
487 procedures (e.g. deviance residual plot and Hosmer- Lemeshow test) will be performed to ensure
488 the adequacy of the final models.

489

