490 Secondary outcomes will be compared between the two treatment groups. For continuous
491 secondary outcomes, we will follow the plan proposed for primary outcome. For discrete
492 secondary outcomes, we will first conduct cross-sectional comparisons based on Chi-squared
493 tests or Fisher's exact test. If the discrete outcome is measured at multiple visits, we will fit
494 repeated measures generalized linear models to simultaneously assess the difference in the
495 longitudinal discrete outcome between the two treatment groups. Other covariates may be
496 included in the models if feasible.

497

498 **Sample Size Calculation and Power Analysis:**

499 This study is generating pilot data for utilization of this procedure in a novel patient population.
500 Given the 15 patients per group, taking into account 20% attrition rate, we would have 12
501 patients per group. In this case, we would have 80% power to detect a difference in glycemic
502 control outcome change that equals 1.2 times the standard deviation of the glycemic control
503 outcome change. The data generated from this study will provide useful relevant preliminary
504 data for planning larger randomized studies.

505

506

507

IV. DATA HANDLING AND RECORD KEEPING:

508 Data collection records with personal identifiers will be stored in locked file cabinets. Blood
509 samples drawn in conjunction with this study will not be labeled with information that could
510 directly identify study subjects. De-identified serum samples will be stored. We may use the
511 samples collected and stored in this study for future studies without a separate IRB consent for
512 the subjects. This will be explained to the study subjects at the time of consent. If we use the
513 samples in future studies, coded identifiers will be used. The informed consent will make it clear
514 that subjects can request their samples to be destroyed at any time. Presentation of the study
515 results at regional or scientific meetings or in publications will not identify subjects. Access to
516 research and confidential records will be limited to clinical investigators, research coordinators,
517 and the IRB at Emory University.
518

519 Study coordinators and/or investigators will collect baseline and follow up data, complete the
520 CRF (case report form) and enter data into RedCap (electronic database provided by the Emory
521 Research Information Technology Department). Baseline data will include demographics

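### The primary safety analysis tests a between-arm difference that can hardly inform Objective 3; the cryoablation-arm rate with an exact interval should take its place

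*Combined protocol and SAP*

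**What the plan says.** Section III.A, Objective 3, is "To determine safety of the cryoablation of the vagus nerve", pursued by monitoring the rates of procedure-related AEs and SAEs. Section III.G defines the endpoint: "The primary safety endpoint of the trial is the occurrence of death and all procedure related" complications, with a list running from bleeding and pneumothorax to gastroparesis and ulceration.

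The analysis in III.G has three steps:
- An unadjusted comparison: "We will first use the Chi-square test (or Fisher's exact test) to compare the occurrence of this" endpoint between the two groups. No rule is given for choosing between the two tests.
- Logistic regression "to evaluate the group difference while adjusting for other potential confounders such as age", gender and BMI.
- A comparison of the number of complications "by using Poisson regression or Negative Binomial regression between the two treatment groups".

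Section III.C puts 15 patients in each arm; Group 1 is "CT guided cryoablation of the vagus nerve plus lifestyle intervention (n=15"). The sample-size text reads "Given the 15 patients per group, taking into account 20% attrition rate, we would have 12" per group and gives power for the glycemic outcome only. Nowhere does the document state an alpha level or sidedness, a confidence interval for a complication rate, or any power or precision for safety.

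**The concern.** All three steps ask whether the arms differ. The most favourable answer they can give the procedure is that no difference was shown, and at this size that answer is expected over a wide range of true complication rates.

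The contrast is also poorly matched to the endpoint. Patients in the lifestyle arm have no procedure, so apart from death they can hardly have a procedure-related complication. That the arms have equal complication rates is then not a hypothesis anyone needs tested. What Objective 3 needs is how often complications occur in those treated, and how high the true rate could still be.

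The data are meant to support a grant application (Section II) and the planning of larger trials (sample-size text). A p-value without a rate and an interval would serve those uses badly.

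**Working it through.** **Inputs.** From the documents: 15 per arm, 12 after 20% attrition, and a binary composite endpoint. Assumed: two-sided alpha 0.05, no control-arm events, and true complication rates shown as a range, because the document gives no composite rate.

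**The plan's own figure.** The only power statement is 80% for 1.2 SD with 12 per arm (15 × 0.8 = 12). A two-sample t-test at two-sided 0.05 (noncentral t) gives 80.2%; one-sided it would give 88.5%. The stated figure is thus reproduced, and it suggests the authors work at two-sided 0.05. There is no safety figure to reproduce.

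**Fisher's test, e events v 0, 15 per arm.** The one-sided p is C(15,e)/C(30,e). With equal arms the two-sided p is twice that.
- e = 3: 455/4,060 = 0.112, two-sided 0.224
- e = 4: 1,365/27,405 = 0.0498, two-sided 0.0996
- e = 5: 3,003/142,506 = 0.0211, two-sided 0.042

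Five of 15 (33%) are therefore needed. With 12 per arm the threshold is also 5 (4 v 0: 0.093; 5 v 0: 0.037). If one control patient has an event, 7 treated patients are needed (6 v 1: 0.080; 7 v 1: 0.035).

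**Power with no control events** is P(X ≥ 5), with X binomial(n, true rate):

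| True rate | n = 15 | n = 12 |
|---|---|---|
| 10% | 1.3% | 0.4% |
| 20% | 16% | 7% |
| 30% | 48% | 28% |
| 40% | 78% | 56% |
| Rate giving 80% power | about 41% | about 50% |

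If events such as infection or nausea were counted in both arms, power stays low: about 17% for 5% v 25% and 15% for 10% v 30%.

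**Dependence on the choice of test, 4 v 0 with 15 per arm.** Uncorrected Chi-square = 30 × (4 × 15)² / (15 × 15 × 4 × 26) = 108,000/23,400 = 4.62, p = 0.032. With Yates correction, p = 0.107. Fisher gives 0.0996 two-sided and 0.0498 one-sided. Expected counts in the event cells are 4/2 = 2, so Fisher is the suitable choice, but the plan does not say so.

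**The regressions.** With no control events the logistic model separates: the group coefficient has no finite maximum-likelihood estimate. A Poisson rate ratio against zero events has the same defect.

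**What an interval would show (exact, Clopper-Pearson).** For 0 of 15, the one-sided 95% upper limit is 1 − 0.05^(1/15) = 18.1%, and the two-sided limit is 1 − 0.025^(1/15) = 21.8%. The two-sided 95% interval is 0.2% to 31.9% for 1 of 15, and 7.8% to 55.1% for 4 of 15. For 0 of 12 the upper limits are 22.1% and 26.5%. Section III.E anticipates individual risks of under 0.5% to under 2%.

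**The case against.** The best defence is that this is a pilot whose safety decisions rest elsewhere. Section III.E has discontinuation limits and a DSMC that reviews AE incidence and severity and advises on interpreting the final safety data. Objective 3 is itself worded as monitoring of rates. All of this stands and limits the severity. It does not supply a final analysis for Objective 3, and a pilot is where estimation serves better than testing.

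A reader might draw several stronger conclusions that the documents do not support:
- *That the plan will call p > 0.05 safe.* It does not say so. It gives no rule of interpretation at all.
- *That Chi-square or Fisher is the only safety analysis.* Regressions are planned too; they share the weakness but they exist.
- *That the test contradicts the stopping rule*, because the trial is discontinued "if 4 participants experience significant AEs (Grade 3" and 4 v 0 is non-significant by two-sided Fisher. That limit counts procedure-related serious AEs of Grade 3, a narrower set than the endpoint. The endpoint count at stopping could exceed 4, and stopping could come before 15 per arm are enrolled. A stopping limit and a final test also need not agree.
- *That harm to a third of patients would probably be missed.* At a true rate of one third with no control events, power is P(X ≥ 5) = 0.596. Non-significance is the likelier outcome only up to about 30%.
- *That a pass/fail margin on the risk difference is needed.* Even 0 v 0 leaves a score (Newcombe) 95% upper limit of 3.84/(15 + 3.84) = 20%, so no margin below that could be met.

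**Conclusion.** The point holds as one of analysis choice. The planned primary safety analysis consists only of between-arm difference tests, for an endpoint that belongs almost wholly to one arm, and it provides no rate or interval.

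The power and p-value figures rest on two-sided 0.05 and no control events, neither of which the document states. One-sided Fisher at 4 v 0 falls just below 0.05, which shows how much turns on the unstated level. The exact bounds for 0 of 15 do not depend on the control arm.

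This is a cheap improvement to the reporting of safety. It does not mean that patients are unprotected during the trial or that the plan states a false inference.

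**What to change.** In Section III.G:
- Make the primary safety analysis the proportion of cryoablation-arm patients with the endpoint, with an exact (Clopper-Pearson) 95% interval.
- Give the between-arm risk difference with a score interval as supportive.
- Make every Chi-square, Fisher or model-based p-value for safety descriptive.
- State that a non-significant result will not be taken as evidence of safety.

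In the sample-size text, add that 0 of 15 treated patients with an event would exclude only true rates above about 18% (one-sided 95%) or 22% (two-sided 95%).

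The cost is a few sentences and one interval calculation, with no new patients, visits or data. The downside is a more modest safety conclusion, since even a complication-free arm leaves rates up to about a fifth possible.

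### Section III.G models procedure-related complications between arms although controls have no procedure: the count model has no finite group effect, and no interval is planned for the treated-arm rate

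*Combined protocol and SAP*

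**What the plan says.** III.G defines the endpoint thus: "The primary safety endpoint of the trial is the occurrence of death and all procedure related" complications, followed by a list that includes bleeding, infection, pneumothorax, dysphagia, gastroparesis, nausea and vomiting. III.B (Endpoints) defines it in the same way. Death carries no attribution wording; the complications do.

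Three between-arm analyses follow in III.G:
- The composite is tested first: "We will first use the Chi-square test", with Fisher's exact test as the alternative.
- The composite is then modelled: "primary safety endpoint between the two treatment groups. We will perform logistic regression", adjusting for covariates such as age, gender and BMI.
- The count of complications, without death, is modelled next: "gender, and BMI. In addition, we will compare the number of procedure related complications", then "by using Poisson regression or Negative Binomial regression between the two treatment groups".

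III.C (Study Design) lists the control arm as "Lifestyle intervention by trained RD/CDE (n=15"). It describes no sham procedure and no matched index date. Objective 3 in III.A concerns the rates of procedure-related AEs and SAEs. Neither III.A, III.B nor III.G plans a confidence interval for that rate, and III.G names no penalised, exact or zero-cell method for the regression models.

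**The concern.** A participant who has no procedure cannot have a complication related to it. If the control count is fixed at zero by definition, the comparison estimates nothing about controls, and the rate ratio that the count model is meant to deliver is infinite or undefined. The quantity that is useful is the complication rate among treated participants and how precisely it is known. That is what Objective 3 concerns, and it is what a larger trial would need; III.G says the data are for planning such trials. As specified, the primary safety endpoint would be summarised by p-values against a structural zero and by models that cannot be fitted in the usual way.

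**Working it through.** **Inputs.** 15 randomised per arm (III.C). Control complication count 0, from the wording in III.B and III.G together with the control arm in III.C, assuming no control has cryoablation during follow-up. Itemised risks in III.E: bleeding <2%, pneumothorax <1%, sedation <0.5%, off-target ablation <1%. The plan gives no power or precision figure for safety. Its only power statement (12 per group, 1.2 SD, 80%) concerns glycemic change. It reproduces at 80.2% with a two-sided 5% t-test (alpha and sidedness assumed) and does not bear on this point.

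**Count model.** With k events in 15 treated, 0 in 15 controls and log rate ratio b, the Poisson log-likelihood maximised over the intercept is, up to a constant,

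l(b) = k·ln(k/15) − k − k·ln(1 + e^(−b)).

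The last term rises towards 0 as b grows and never reaches it, so there is no finite maximum for any k ≥ 1. For k = 5, l(b) is:

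| b | l(b) |
|---|---|
| 0 | −13.959 |
| 5 | −10.527 |
| 10 | −10.4933 |
| 20 | −10.4931 |

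What software prints depends on where it stops. For k = 3 an iterative fit gives a log rate ratio of 6.4 (SE 8.6) after 5 iterations, 11.4 (SE 104) after 10 and 26.4 (SE about 188,000) after 25. The negative binomial model with a log link has the same zero-mean problem. For k = 0 the rate ratio is 0/0 and the fit fails.

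The likelihood-ratio test survives. For k = 5 the statistic is 2 × (13.959 − 10.493) = 6.93, p=0.0085. What fails is the point estimate and its Wald inference.

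**How likely is k = 0?** Summing the four risks at their limits gives 2 + 1 + 0.5 + 1 = 4.5%. This assumes that they do not overlap and leaves out milder listed events such as nausea. Then P(0 of 15) = 0.955^15 = 0.50. Over a range of true rates: 74% at 2%, 46% at 5%, 21% at 10%.

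**Logistic model for the composite (group term only).** With 3/15 treated and no control death, the control log-odds are minus infinity; software returned a coefficient of 21.2 with SE 12,444. With one control death the estimate is finite: ln[(3/12)/(1/14)] = ln 3.5 = 1.25, SE = √(1/3 + 1/12 + 1 + 1/14) = 1.22.

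**Two-by-two tests named in III.G.**

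| Treated v control | Fisher p | Uncorrected chi-square p |
|---|---|---|
| 3/15 v 0/15 | 0.224 | 0.068 |
| 4/15 v 0/15 | 0.0996 | 0.032 |
| 5/15 v 0/15 | 0.042 | 0.014 |
| 6/15 v 1/15 | 0.080 | 0.031 |

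The two tests fall on opposite sides of 0.05 in the second and fourth rows. In the second row the expected event count is 4/2 = 2 per arm, which favours Fisher.

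**The missing interval.** Clopper-Pearson 95% for 0/15: the upper limit is 1 − 0.025^(1/15) = 21.8%. By the same method 3/15 gives 4.3-48.1% and 4/15 gives 7.8-55.1%.

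**The case against.** The strongest reply is that the listed events include infection, nausea and vomiting, and dysphagia, over the whole study. Controls can have all of these. A comparison adjusted for age, gender and BMI makes sense if they are counted in both arms whatever their cause, and the models could then be fitted. That may be what was intended, but III.B and III.G both restrict the complications to procedure-related ones, Objective 3 does likewise, and III.G has no rule for attributing an event in a control. So III.G needs a wording change on either reading. A sentence in III.C on where the procedure takes place refers to all subjects. It conflicts with the lifestyle-alone arm in the same section and must be reconciled, but it does not rescue the comparison.

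It is also fair to say that the harm is limited. The treated count and denominator would let a reader compute the interval, AEs are recorded regardless of relatedness (III.E), and this is an exploratory pilot. That bears on severity, not on whether the stated analysis works.

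A reader might infer several stronger things that the documents do not support:
- That no safety test can be computed. The chi-square, Fisher and likelihood-ratio tests all can.
- That 5 treated events (or 7, if one control dies) are needed for significance. That holds for Fisher only; uncorrected chi-square, the test named first, crosses 0.05 at 4/15 v 0/15 and at 6/15 v 1/15.
- That "Standard model selection (e.g. forward, backward variable selection) and model checking" would remove the treatment term. III.G does not say that selection uses Wald p-values or that group may be dropped; the natural reading keeps group and selects covariates.
- That the plan treats a non-significant result as proof of safety. III.G does not say so.
- That only 12 may be treated. III.D defers the procedure for high glucose and does not cancel it; the 12 per group in III.G is a post-attrition number for the glycemic outcome.

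**Conclusion.** The point holds on the text as written. The between-arm count model has no finite group effect when there are treated events, and none that is identified when there are not. The second case has roughly even odds under the assumed 4.5% total risk, and a 21% to 74% chance for true rates from 10% down to 2%. The logistic model shares the problem unless a control dies. The two-by-two tests work but answer a question whose control side is fixed by definition, and the choice left open between them can change the result. The planned analysis gives no interval for the rate that Objective 3 concerns, and at this sample size the uncertainty is large: no events in 15 would still be compatible with a rate of up to 21.8%. The conclusion rests on the procedure-related wording and on controls having no cryoablation. It should be fixed before analysis. It does not touch the efficacy analysis, the stopping rule or the committee's safety review, none of which uses these tests.

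**What to change.** In III.G:
- Drop the between-arm Poisson or negative binomial model for procedure-related complications.
- Make the main safety analysis the incidence of procedure-related complications among all participants who had cryoablation, including those later withdrawn, overall and by component, with Clopper-Pearson 95% intervals.
- Report the III.B composite (death or procedure-related complication) as a count and proportion with an exact 95% interval in each arm, and list deaths by arm, in place of the adjusted logistic model. The endpoint then keeps an analysis.
- Make any between-arm comparison on all adverse events regardless of attribution, by Fisher's exact test, labelled supportive. State that the cryoablation arm has extra contacts, namely a "call 24 hour post-procedure to evaluate for any immediate complications, 1 week in person" visit and a 2-month safety call, which may raise ascertainment in that arm.
- If the listed events were meant to be counted whatever their cause, say so explicitly.

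The cost is a wording change. No new data are needed, because AEs are asked about at every visit (III.C) and documented whether or not related (III.E). The price is candour about precision: the intervals are wide, and the all-AE comparison remains open to unequal ascertainment.
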